Influence of body position on the defecation model measured during high resolution anorectal manometry in children: a controlled study.

Department of Paediatric Gastroenterology and Nutrition, Medical University of Warsaw, Poland

ABSTRACT

Background

Functional disorders of the lower gastrointestinal tract, including constipation, are one of the most frequent reasons for consultations with a paediatric gastroenterologist. Three-dimensional high-resolution anorectal manometry (3D HR-ARM) is a non-invasive test, performed by placing a catheter with numerous pressure sensors to the rectum. It allows to assess the function of the lower gastrointestinal tract. 3D HR-ARM may disclose impaired relaxation or paradoxical contraction of the pelvic floor muscles and/or inadequate propulsive forces during bear down manoeuvre - this is called dyssynergic defecation. It is suspected that dyssynergic defecation may be a cause of constipation in a significant percentage of patients.

Nowadays 3D HR-ARM is provided in a supine position, although the study in healthy adults using an anorectal catheter showed that the percentage of abnormal results during bear down manoeuvre in the supine position can reach as much as 67-87%. Such a high percentage of false positive results may result from a non-physiological position during the examination. Assessment of 3D HR-ARM results in the paediatric population requires validation in a sitting position.

The aim of the study is to assess the influence of body position on parameters of bear down manoeuvre during 3D HR-ARM in children with constipation in comparison with healthy volunteers.

Methods

This is an open, prospective study. Study participant aged 5-18 years, will be divided into two groups: I. patients with constipation diagnosed according to the Rome IV criteria and II. healthy controls. The study population will have no history of surgery due to congenital anomalies in lower gastrointestinal tract, inflammatory bowel diseases or inflammation of the large intestine with a different aetiology, anal fissure, inflammation of the anal area or other conditions which, in the opinion of the researcher, could affect the functioning of the distal gastrointestinal tract.

The test will be performed both in supine and sitting position successively, using 3D HR-ARM. Resting, squeeze pressures, and bear down manoeuvre variables will be obtained. Diagnosis of dyssynergic defecation requires $\leq 20\%$ relaxation of anal sphincter and/or intrarectal pressure ≥ 40 mmHg during bear down manoeuvre.

There should be 30 people in the constipation group and healthy controls. Due to possible differences depending on age, it was decided to conduct the study in two separate age groups: I. 5-10 years old, and II. 11-18 years old. The total number of patients in the study will therefore be 120 people.

The primary end point of the study will be the assessment of difference in number of patients with dyssynergic defecation in sitting and lying position.

The study was approved by the Ethics Committee of the Medical University of Warsaw, Poland (KB/178/2019).

BACKGROUND

Functional disorders of the lower gastrointestinal tract, including **constipation**, are frequent reasons for consultations with paediatric gastroenterologist [1]. Anorectal manometry is a non-invasive, standardized test performed by placing a catheter with numerous pressure sensors to the rectum. It allows to assess the function of the lower gastrointestinal (GI) tract by measurement of pressure activity in this area [2]. It can be used to diagnose functional disorders of lower GI (such as constipation, faecal incontinence), congenital anomalies (i.e. Hirschsprung's disease). Anorectal manometry is also useful in postoperative evaluation of sphincter function in patients with congenital defects such as Hirschsprung disease or anorectal atresia.

Three-dimensional high-resolution anorectal manometry (3D HR-ARM) is the most advanced system of anorectal manometry used in clinical practice. In this project, will be used catheter (Manoscan 360 3D, Medtronic, Duluth, USA) that provide a continuous and dynamic spatiotemporal mapping of anorectal pressures [3]. This system operates with rigid probe of a greater diameter. The catheter consists of 256 sensors that asses longitudinally and circumferentially pressure in the rectum and is able to produce detailed three-dimensional maps of obtained results. This allows for more detailed data acquisition and easier interpretation of results. There is a lumen inside the probe through which air can be administered into the balloon (3.3 cm in length), allowing for the measurement of the rectoanal inhibitory reflex (RAIR) and intrarectal pressure. Resting pressure, maximum squeeze pressure, canal length, bear down manoeuvre variables (such as percentage of anal relaxation rate, residual anal pressure, rectoanal pressure gradient, intrarectal pressure), RAIR is measured during each test. The catheter is connected to a recorder and amplifier system (ManoScan A120; Medtronic, Duluth, USA).

So far, 3D HR-ARM is provided in lying (supine or left lateral) position. Experience of our Department show that supine position with maintained eye to eye contact between patient and doctor providing the test, allows to easier cooperation during examination. It is crucial (specially with younger

patients) to alleviate stress during the procedure. Every subsequent part of the protocol is explained before the start and verbal instructions during manoeuvres are served. It has been proved to influence results in adults [4]. Another very important aspect of this examination is ensuring intimate examination conditions (one patient in examination room, close parent presence during whole time).

Despite the simplicity of the manometric test and easiness of data interpretation, most of the research on standards or influence of age and sex on anorectal manometry parameters were performed on the adult population. Moreover, the manometry catheters used to collect data were less advanced than 3D HR-ARM [5]. Recently the number of conducted researches on this topic in the paediatric population is increasing. Our department is playing a significant role in the field of research on 3D HR-ARM. In the last few years, our team published several papers on 3D HR-ARM including results of study on cut-off values for diagnosis of dyssynergic defecation (DD) in children [6].

The abnormal defecation dynamics model may be revealed in detail using 3D HR-ARM, which may disclose impaired relaxation or paradoxical contraction of the pelvic floor muscles and/or inadequate propulsive forces during bearing down manoeuvre – this is diagnosed as DD[7]. It is suspected that dyssynergia of the pelvic floor during defecation may be a cause of constipation in a significant percentage of patients [8][9].

So far only a few studies have been performed comparing the pressure values during bear down manoeuvre in both sitting and lying positions. Those studies were carried out in adults. In the study by Rao et al. healthy volunteers presented DD in the supine position significantly more frequently than in the sitting position (36% vs 20%) [10]. The study by Su et al. showed that a propulsive force that was too low was the cause of false-positive results [11]. In the study by Wu et al.[12] the sitting position not only significantly affected the propulsive force, but also had a significant impact on the percentage of anal canal relaxation and rectoanal pressure gradient during bear down manoeuvre. Patients with constipation significantly more often presented the inadequate relaxation of the anal canal, which was more visible in the sitting position. It has been shown that the rectoanal pressure gradient evaluated in the sitting (but not lying) position and significantly correlates with the effective defecation assessed on the balloon expulsion test.

The study in healthy adults using 3D HR-ARM showed that the percentage of abnormal results during bear down manoeuvre in the supine position can reach as much as 67-87% [13][14]. Such a high percentage of false positive results may result from a non-physiological position during the examination. Assessment of 3D HR-ARM results obtained in the paediatric population requires validation in a sitting position.

The aforementioned studies are first milestones in the field that suggest revision of the position in which 3D HR-ARM is performed per protocol. Thus far no similar scientific research has been performed in children. Moreover, the reference values of registered pressures during 3D HR-ARM in people without constipation were not specified, which would allow for a more precise diagnosis of patients with an incorrect defecation model and a precise selection of patients who could benefit from a certain type of treatment, for example biofeedback therapy.

RESEARCH OBJECTIVE

The assessment of the influence of body position on manometric parameters of bear down manoeuvre during 3D HR-ARM in paediatric patients with functional constipation compared to healthy volunteers.

METHODS

The study will be prospective with a defined study group and control group.

Inclusion criteria – the study group:

- age from 5 to 18 years old
- functional constipation diagnosed on the basis of Rome IV criteria
- parental or guardian written consent to the participation of the child in the study; in the case of a child ≥ 16 years old also the child's written consent

Inclusion criteria – the control group:

- age from 5 to 18 years old
- no lower gastrointestinal symptoms
- parental or guardian written consent to the participation of the child in the study; in the case of a child ≥ 16 years old also the child's written consent

Exclusion criteria – the study group and the control group:

- undergone surgeries due to congenital anomalies in the lower gastrointestinal tract
- inflammatory bowel diseases or inflammation of the large intestine with a different aetiology
- anal fissure, inflammation of the anal area or other conditions which, in the opinion of the researcher, could affect the functioning of the distal gastrointestinal tract

SAMPLE SIZE

The sample size was calculated to detect a 45% difference in the percentage of patients with a negative rectoanal gradient, assuming equal groups, alpha = 0.05, beta = 0.1, and a 30% drop out percentage. There should be 30 people in the constipation group and 30 healthy volunteers.

Due to possible differences depending on age, it was decided to conduct the study in two separate age groups (I. younger, i.e. 5-10 years old and II. older, 11-18 years old). The total number of patients in the study will therefore be 120 people.

END POINTS

Primary end point:

The difference in the number of patients with DD (defined as $\leq 20\%$ relaxation of anal sphincter and/or intrarectal pressure ≥ 40 mmHg during bear down manoeuvre) in sitting and lying position.

Secondary end point:

Values of manometric parameters obtained in the lying and sitting position, i.e.:

- mean resting pressure of the anal sphincter (mmHg)
- maximum squeeze pressure (mmHg)
- mean anal canal length (cm)
- the assessment of parameters of defecation dynamics during HR-ARM: percentage of anal relaxation rate, residual anal pressure, rectoanal pressure gradient.

All secondary end points will be assessed in sitting and lying position in the two groups.

LOCATION

The Department of Paediatric Gastroenterology and Nutrition, Medical University of Warsaw.

INTERVENTION

The parents of children who are patients of the Department of Paediatric Gastroenterology and Nutrition, who meet the inclusion criteria will be offered the option to participate in the study. After the physical examination and the anthropometric measurements, the 3D HR-ARM will be performed in the lying and then in the sitting position.

In all cases, the condition for enrolment will be obtaining the written consent of the child's parents or guardians, or in the case of a child ≥ 16 years old also the child's consent.

ETHICAL CONSIDERATION

Before starting, it will be explained to parents and children how the manometry will be performed. Full privacy will be maintained during the manometric procedure.

The study was approved by the Ethics Committee of the Medical University of Warsaw, Poland (KB/178/2019).

EXPECTED BENEFITS

The test will determine the reference pressure values recorded during bear down manoeuvre in the lying and sitting position. This will improve adequacy of diagnosis of DD in patients with functional constipation as well as the choice of the appropriate treatment method, for example biofeedback therapy.

RISK AND INCOVENIENCES FOR PATIENTS:

The participation in the study will be similar to a routine hospitalization of patients with constipation in our Department. In addition to routine examinations performed as a part of the hospitalization, the HR-ARM in the lying and then the sitting position will be performed. During the test the patient may experience anal discomfort. After examination, lower gastrointestinal bleeding may occur, but it's extremely rare.

THE FIELD AND DISCIPLINE OF KNOWLEDGE:

Field: medical sciences and health sciences

Discipline: medical sciences

Speciality: paediatric gastroenterology

FUNDING SOURCE:

12 000 PLN - manometric disposable sheaths

300 PLN - stationery

10 000 PLN - publications cost

Source: Statutory money of Department of Paediatric Gastroenterology and Nutrition.

References:

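### The only sample-size calculation is for negative rectoanal gradient, not for the primary end point (DD sitting versus lying in the same child), so its 90% power does not apply there

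*Protocol*

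**What the plan says.** The Sample Size section of the protocol holds the only calculation: "The sample size was calculated to detect a 45% difference in the percentage of patients with a negative rectoanal gradient, assuming equal groups", with alpha 0.05, beta 0.1 and 30% drop-out. The result is "There should be 30 people in the constipation group and 30 healthy volunteers". Because results may depend on age, "it was decided to conduct the study in two separate age groups", which doubles 60 to 120.

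Under End Points, the primary end point is "The difference in the number of patients with DD" between the sitting and lying positions. DD is defined by a threshold on "relaxation of anal sphincter and/or intrarectal pressure ≥ 40 mmHg during bear down manoeuvre". The rectoanal gradient appears only in the secondary list, among "percentage of anal relaxation rate, residual anal pressure, rectoanal pressure gradient". The Background also names it separately from the two components of DD: "percentage of anal relaxation rate, residual anal pressure, rectoanal pressure gradient, intrarectal pressure".

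The abstract and the Intervention section say that each child is examined lying and then sitting.

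**The concern.** The sizing variable and the primary variable differ, and so, apparently, does the type of comparison. The gradient is no part of the DD definition. Even in the secondary list it stands as a measured value, so the proportion with a negative gradient is not itself a listed end point. The primary contrast is within child. Its power depends on how many children change status between positions, and the protocol gives no assumption on that.

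The 45% is also hard to interpret. The section does not say which two percentages differ, what their base rates are, or in which position the gradient is taken. Yet the Background reports that sitting had a "significant impact on the percentage of anal canal relaxation and rectoanal pressure gradient during bear down manoeuvre". The equal groups of 30 and 30 suggest constipated versus healthy children, but that is an inference.

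At stake is whether 120 children are justified for the main question, and how a null primary result would be read. A reader could credit it with 90% power that was never calculated for it.

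**Working it through.** **Inputs.** From Sample Size: alpha 0.05 (sidedness not stated; two-sided assumed), power 90%, a 45-point difference, 30% drop-out, 30 per group per age stratum, 120 in total. From Background: DD in 36% lying and 20% sitting, in healthy adults. These are the only DD rates by position in the protocol and serve as illustration. Discordance is not stated, so it is varied.

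**1. The plan's own figure.** For two independent proportions (pooled form):

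n per group = [1.960·√(2p̄(1−p̄)) + 1.282·√(p₁(1−p₁)+p₂(1−p₂))]² / 0.45²

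| Rates | n | After 30% loss (n/0.7) |
|---|---|---|
| 0% vs 45% | 15.9 → 16 | 23 |
| 10% vs 55% | 20.6 → 21 | 30 |
| 27.5% vs 72.5% | 23.8 → 24 | 35 |

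For 10% vs 55%: (1.960·0.662 + 1.282·0.581)²/0.2025 = 4.173/0.2025 = 20.6. The unpooled form gives 13–21, or 19–30 after loss. So 30 per group fits an unpaired comparison of groups. It cannot be confirmed without the base rates, and it does not prove which comparison was meant. No arithmetic error is alleged.

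**2. Evaluable children after 30% loss.**
- All children: 120 × 0.7 = 84.
- One group over both ages, or one age stratum with both groups: 60 × 0.7 = 42.
- One group in one age stratum: 30 × 0.7 = 21.

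**3. Paired power at 36% vs 20%.** Let p₁₀ be the share with DD only when lying and p₀₁ the share with DD only when sitting (reverse discordance). Then p₁₀ − p₀₁ = 0.16, and p₀₁ lies between 0 and 0.20, the sitting rate. Independence of the two positions gives p₀₁ = 0.64 × 0.20 = 0.128.

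Power = Σₘ Bin(m; n, p₁₀+p₀₁) × P(McNemar p ≤ 0.05 given m discordant pairs)

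| p₀₁ | 0 | 5% | 10% | 12.8% | 20% |
|---|---|---|---|---|---|
| Exact, 21 pairs | 10.6% | 12.8% | 12.2% | 11.5% | 9.8% |
| Exact, 42 pairs | 68.3% | 43.0% | 32.3% | 28.6% | 21.3% |
| Exact, 84 pairs | 99.5% | 80.4% | 63.2% | 56.8% | 45.3% |
| Mid-p, 21 pairs | 23.7% | 22.6% | 19.4% | 17.7% | 14.5% |
| Mid-p, 42 pairs | 82.4% | 53.1% | 40.5% | 35.6% | 26.6% |
| Mid-p, 84 pairs | 99.9% | 85.1% | 69.1% | 62.6% | 50.4% |

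The first cell can be checked by hand. The exact test needs at least 6 discordant pairs (2 × 0.5⁶ = 0.031; with 5 it is 0.0625), while 21 × 0.16 = 3.4 are expected.

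**4. If the paired DD change were itself 45 points.** Over every possible reverse discordance (0–27.5%), exact power is 46–96% with 21 pairs, 83–100% with 42 and 99–100% with 84.

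**5. Paired difference detectable at 90% power, exact test, in percentage points.**

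| p₀₁ | 0 | 5% | 10% | 15% |
|---|---|---|---|---|
| 21 pairs | 39.7 | 52.3 | 59.8 | 66.3 |
| 42 pairs | 21.0 | 31.0 | 37.6 | 42.6 |
| 84 pairs | 10.8 | 19.0 | 23.5 | 26.8 |

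**The case against.** The mismatch itself is hard to dispute; the case on the other side concerns its weight.

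- **Discordance.** Values above independence imply that DD in one position makes DD in the other less likely, which is implausible. Stopping at 12.8%, exact power at 36% vs 20% is 57–99.5% with 84 pairs and 29–68% with 42. For a 45-point change, independence allows at most 0.275 × 0.275 = 7.6%. Up to there, power is 75–96% with 21 pairs, at least 98% with 42, and about 100% with 84. This is fair, and the low ends above should be read as bounds.
- **Population.** The primary end point names no subgroup, and assessment in the two groups is tied to the secondary end points. The 21-pair reading therefore has the least support in the text. An age-stratum reading (42 pairs) is arguable, because the study is to be conducted in separate age groups. The protocol does not settle it.
- **Effect size.** The 36% and 20% come from healthy adults. The Background also cites 67–87% abnormal supine results in healthy adults. Those are not paired positional rates, but they leave room for a change well above 16 points.
- **SAP.** The test and the analysis population are often left to a SAP, and none was available. That does not answer the point: the protocol does state a basis for its sample size, and that basis is another variable.

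These points rule out a claim that the trial is underpowered. None of them carries the 90% over to the primary end point. Reading the 45% as a sitting-versus-lying contrast would not do so either, because the variable would still not be DD.

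**Conclusion.** The concern holds and should be fixed. The one stated power figure belongs to a variable outside the primary end point, and the protocol justifies 120 children for no primary comparison. This rests on the text alone and needs no assumption.

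The size of the consequence is open. It depends on the true DD rates, the discordance, the test and the population compared, and the same recruitment can give anything from very low power (one group in one age stratum, a 16-point change) to near-certain power (all children, a 45-point change). The illustrations assume a two-sided 5% test, 30% loss and adult rates. They show why the figure has to be stated; they do not predict the result.

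**What to change.** Keep 120 children and rewrite the Sample Size section so that it:

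1. addresses DD lying versus sitting as a paired comparison;
2. names the population on which the primary comparison rests: all children, each age stratum, each group, or each group within each age stratum;
3. gives the power or detectable paired difference there, under the sponsor's own assumed lying and sitting DD rates, discordance and test;
4. says which two percentages, base rates and position the 45% refers to, and that the 45-point, 90% statement concerns only negative rectoanal gradient.

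The detectable differences tabulated above show the form such a statement could take; they are not proposed values.

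The cost is rewording, with no extra patients. The stated power or detectable difference may become less favourable, most of all if the comparison is made in each group within each age stratum.

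### The primary end point counts a high intrarectal pressure (≥ 40 mmHg) as dyssynergic defecation, the opposite of the protocol's own concept of inadequate propulsion, so the lying-versus-sitting effect is distorted and can change sign

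*Protocol*

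**What the plan says.** The concept of DD appears twice in the protocol. The Abstract (Background paragraph) names impaired relaxation or paradoxical contraction and/or "inadequate propulsive forces during bear down manoeuvre - this is called dyssynergic defecation". The Background section repeats it: "impaired relaxation or paradoxical contraction of the pelvic floor muscles and/or inadequate propulsive forces during bearing down manoeuvre – this is diagnosed as DD". The Background also reports, from an earlier adult study, that "a propulsive force that was too low was the cause of false-positive results".

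The operational rule also appears twice, in the Abstract (Methods) and under End points, Primary end point. Both require at most 20% "relaxation of anal sphincter and/or intrarectal pressure ≥ 40 mmHg during bear down manoeuvre". The primary end point is the difference between sitting and lying in the number of patients who meet this rule.

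**The concern.** Concept and rule share a structure: a relaxation criterion and a push criterion, joined by and/or. The push criterion points in opposite directions. In the concept the abnormality is too little force; in the rule it is a pressure at or above a threshold. Because of the and/or, high pressure alone is enough to make a child DD.

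Children who fail the relaxation criterion are DD whichever way the pressure inequality runs. The error therefore touches only children with relaxation above 20%, but for them it turns the classification into its exact complement. Since the rule classifies every child in both positions, the primary comparison is at stake. Among children with relaxation above 20% in both positions, the position effect is reversed. In the whole sample it can reverse, shrink or be overstated, depending on how relaxation failure changes with position. The Background says, of another adult study, that sitting "also had a significant impact on the percentage of anal canal relaxation". It does not say in which direction sitting changes propulsive force, so the direction of the distortion cannot be predicted.

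**Working it through.** The protocol gives no expected DD rate under its own rule, so there is no plan figure to reproduce. The sample size is built on a different variable (negative rectoanal gradient) and is not part of this point.

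**Step 1: the identity.** Let A be relaxation ≤ 20% and B be intrarectal pressure ≥ 40 mmHg. In either position:

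- DD rate as written = P(A or B)
- DD rate with the inequality reversed (the intended rule) = P(A or not B)
- Sum = 2P(A) + P(not A) = 1 + P(A)

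This needs no assumption about independence or distributions. Take effects as sitting minus lying, and let r be the rate of relaxation failure:

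- effect as written = (r sitting − r lying) − intended effect

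The two effects share a sign only if relaxation failure moves in the same direction as the intended effect, and by more than it.

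**Step 2: the cited adult rates.** The Background quotes 36% DD supine and 20% sitting in healthy adult volunteers. *Assumption: these rates hold in this trial's controls under the intended rule.* The intended effect is 20 − 36 = −16 points.

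- Rates as written: at least 100 − 36 = 64% lying and 100 − 20 = 80% sitting.
- In 60 healthy controls (30 in each of two age groups): at least 0.64 × 60 = 38.4 lying and 0.80 × 60 = 48 sitting. The intended rule gives 0.36 × 60 = 21.6 and 0.20 × 60 = 12.

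| Change in relaxation failure, sitting minus lying | Effect as written |
|---|---|
| 0 | 0 + 16 = +16 |
| −10 | −10 + 16 = +6 |
| −16 | −16 + 16 = 0 |
| −25 | −25 + 16 = −9 |

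Relaxation failure cannot exceed total DD, so r lying lies between 0 and 36 and r sitting between 0 and 20. The change then runs from −36 to +20, and the effect as written from −20 to +36.

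**Step 3: dependence on the rates chosen.** The Background also cites 67–87% abnormal supine results in healthy adults with 3D HR-ARM, the technique used here. If that were the intended DD rate lying, the lower bound as written would be 100 − 87 = 13% to 100 − 67 = 33%, or about 8 to 20 of 60 controls (0.13 × 60 = 7.8; 0.33 × 60 = 19.8). The counts move a great deal with the rate chosen; the identity does not.

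**Step 4: two model illustrations.** *All inputs are assumed*: pressure normal with SD 15 mmHg and independent of relaxation. As written, P(DD) = 1 − (1 − r) × P(pressure < 40); reversed, P(DD) = 1 − (1 − r) × P(pressure ≥ 40).

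- *Relaxation failure 30% in both positions, mean pressure 35 lying and 50 sitting.* P(pressure < 40) is 0.631 lying and 0.252 sitting. As written: 1 − 0.7 × 0.631 = 55.9% and 1 − 0.7 × 0.252 = 82.3%, effect +26. Reversed: 74.1% and 47.7%, effect −26. The sign flips exactly.
- *Relaxation failure 60% lying and 30% sitting, mean pressure 30 lying and 40 sitting.* P(pressure < 40) is 0.748 and 0.500. As written: 1 − 0.4 × 0.748 = 70.1% and 1 − 0.7 × 0.5 = 65.0%, effect −5. Reversed: 89.9% and 65.0%, effect −25. The sign is kept, but most of the effect is lost.

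Both agree with the identity: 0 − (−26) = +26 and −30 − (−25) = −5.

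**The case against.** - **Intrarectal pressure as the measure of push.** The protocol never says outright that intrarectal pressure measures propulsive force. This is an inference from the matching two-part structure and from the bear-down variables listed in the Background, which offer no other direct measure of push. It is a strong inference, but it should be stated as one.
- **High pressure as a qualifier.** The threshold might have been meant as a condition of adequate push accompanying failed relaxation. That would need and, not and/or; as written, pressure alone suffices. The rule is wrong on this reading too.
- **The numbers.** The 36% and 20% come from one adult study whose DD rule the protocol does not give, and the 3D HR-ARM figures lead to quite different counts. The model inputs are chosen by hand, and relaxation failure of 60% lying is incompatible with total DD of 36%. This stands: the figures show what can happen and do not estimate what will happen.
- **A sign slip that can be undone.** It may well be a slip, and the recorded pressures allow reclassification. That limits the harm. But the same text stands in both places, with no correct version to fall back on, and correcting it after results are known would be a post hoc change to the primary end point.

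**Conclusion.** The concern holds. The rule for the primary end point contradicts the protocol's own concept of DD, and this follows from the text, given that intrarectal pressure stands for propulsive force. The relation between the two effects is exact: effect as written = change in relaxation failure minus intended effect. If relaxation failure does not differ by position, the result is fully reversed.

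The size is conditional. Using the cited adult rates as if they applied under the intended rule, −16 points becomes +16 with unchanged relaxation failure, within a possible range of −20 to +36. The protocol gives no paediatric pressure distribution, so neither the size nor the certainty of a sign change can be established from it. The definition must be corrected before the primary end point is analysed.

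**What to change.** Reconcile the pressure criterion in the Abstract (Methods) and in End points, Primary end point, with the concept in the Abstract (Background) and the Background section, so that it expresses inadequate propulsion: below, rather than at or above, the stated 40 mmHg. The investigators should confirm the direction, the cut-point and how a value of exactly 40 mmHg is treated before children are classified. It would help to state that intrarectal pressure is the measure of propulsive force. Any child already classified under the written rule should be reclassified.

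The cost is one line in each of two places. No new data are needed, since the Background lists among the variables "rectoanal pressure gradient, intrarectal pressure), RAIR is measured during each test". The protocol records ethics approval, so the investigators should check whether the correction needs a formal amendment.

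### Every child is tested lying first and sitting second, so the primary position effect cannot be separated from an effect of test order

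*Protocol*

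**What the plan says.** The Intervention section of the protocol states that "the 3D HR-ARM will be performed in the lying and then in the sitting position". The section on risks and inconveniences repeats the sequence: "the HR-ARM in the lying and then the sitting position will be performed". The abstract says only that "The test will be performed both in supine and sitting position successively". The protocol mentions no random or alternating order, no familiarisation run, no repeat lying test and no rest interval between the two recordings.

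The research objective is "The assessment of the influence of body position on manometric parameters of bear down manoeuvre during 3D HR-ARM", in constipated children compared with healthy volunteers. The primary end point is "The difference in the number of patients with DD" between sitting and lying, which is a within-child comparison. The Background section calls the relief of stress crucial, especially in younger patients, and says of coaching: "verbal instructions during manoeuvres are served. It has been proved to influence results in adults".

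**The concern.** Bearing down is a voluntary effort made on instruction. When a child reaches the sitting recording, he or she has already been through a full lying recording with the probe in place and with coaching. The child may by then be more practised and calmer, or more tired and uncomfortable. Because sitting always comes second, any such change is counted as an effect of sitting.

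Practice or habituation would lower the DD rate at the second test, which is the direction the Background section leads one to expect. Fatigue or discomfort would work the other way and could hide a real benefit. The trial could therefore report a position effect that is an artefact of order, or miss a true one. The Expected Benefits section also intends to derive reference values for both positions, so the sitting values would carry the same second-test component into diagnostic use.

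**Working it through.** **1. The plan's own figure.** The protocol gives no figure for an order effect. Its only calculation is the sample size, which is to "detect a 45% difference in the percentage of patients with a negative rectoanal gradient" with alpha 0.05, beta 0.1 and 30% drop-out, giving 30 per group. The two rates are not stated. One pair that reproduces it is 0.55 versus 0.10 (mean 0.325), two-sided, without continuity correction:

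n = [1.960·√(2·0.325·0.675) + 1.282·√(0.55·0.45 + 0.10·0.90)]² / 0.45² = (1.298 + 0.745)² / 0.2025 ≈ 20.6, rounded up to 21; 21/0.7 = 30.

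Other pairs 45 points apart give 28 to 35 per group. So 30 is attainable, but nothing in the order problem depends on it.

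**2. Identifiability.** Let π be the change in the DD rate due to sitting rather than lying, and ω the change due to being tested second rather than first.

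- Lying then sitting: expected (sitting − lying) = π + ω.
- Sitting then lying: expected (sitting − lying) = π − ω.

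The protocol has only the first sequence, so there is one equation with two unknowns. With both sequences in equal numbers, the average of the two lines is π, and half their difference is ω.

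**3. The control group.** Controls follow the same order. The contrast between groups is (π_constipated + ω_constipated) − (π_healthy + ω_healthy). The order terms cancel here only if they are equal in the two groups, and this contrast is not the primary end point. The primary sitting-versus-lying difference keeps ω in full.

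**4. Illustration of size.** These inputs are assumptions, not protocol figures:

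- True position effect: zero.
- Chance reclassification: 10% of children in each direction.
- Order effect: lowers DD at the second test by k points.
- Test: exact two-sided McNemar at 0.05.

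Fixed order: P(DD lying only) = 0.10 + k and P(DD sitting only) = 0.10. Order counterbalanced 1:1: both probabilities are 0.10 + k/2, because half the children carry the order effect in each direction.

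The rejection probability is the sum, over the number m of discordant children ~ Binomial(n, sum of the two probabilities), of the chance that the exact test on m rejects. The sizes 30, 60 and 120 are one cell, one age band and the whole study. The sizes 21, 42 and 84 are the same after the planned 30% drop-out (0.7 × 30, 0.7 × 60, 0.7 × 120).

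| Order effect k | n=21 | n=30 | n=42 | n=60 | n=84 | n=120 |
|---|---|---|---|---|---|---|
| 5 points | 1.8% | 3.5% | 5.2% | 7.6% | 10.3% | 14.3% |
| 10 points | 5.1% | 9.2% | 14.2% | 22.1% | 31.0% | 45.4% |
| 16 points | 12.2% | 20.7% | 32.3% | 46.9% | 63.2% | 81.5% |
| 20 points | 18.8% | 30.7% | 46.4% | 63.5% | 80.3% | 93.4% |

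In the counterbalanced design with the same k, no entry exceeds 3.6%. The 16-point row equals the adult supine-versus-sitting difference cited in the Background section (36% − 20%) and is there for scale only.

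**5. Sensitivity.** If total discordance is instead held at 30%, the fixed-order rates at n = 120 are about 13%, 46%, 88% and 99% for k = 5, 10, 16 and 20. The pattern is the same. In every row a larger study makes it more likely that an order effect is declared a position effect.

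**The case against.** Nothing in the protocol shows that an order effect exists. The sentence on verbal instruction concerns how the test is coached, not repeat testing, and the lying recording is coached too, so instruction alone need not create a change from first to second test. The direction is open. An artefact of 20 points would exceed the whole adult position effect that the protocol cites. Rates at 120 children also flatter the point: the planned numbers include 30% drop-out, and the protocol speaks of two separate age groups without specifying a pooled test. Finally, the objective includes a comparison with healthy volunteers, in which an equal order effect would cancel.

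Most of this stands as a limit on the illustration, which is why the table includes 5 points and the sizes after drop-out. In a single cell of 21 children the false-attribution rate is modest for small order effects. The control-group argument is valid for the position-by-group contrast, under the untestable condition of equal order effects. None of it touches the primary end point, where position and order are the same variable. The burden also lies with the design: having fixed the order, the trial will produce no data that could show the order effect to be small.

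**Conclusion.** The concern holds. As designed, the primary result cannot be attributed to body position, because the bias equals the whole order effect in percentage points, whatever that is. This follows from the single fixed sequence and needs no assumption. It cannot be repaired in a later analysis plan.

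The size of the practical risk does rest on assumptions about discordance and order effect. For a 10-point order effect and no true position effect, a spurious significant finding occurs in about 14% of studies at 42 evaluable children and 31% at 84, against about 3% with counterbalanced order. Because the flaw affects the primary question and is irreversible once data are collected, it should be corrected before testing goes further.

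**What to change.** Randomise the order of positions (lying–sitting or sitting–lying) 1:1 in blocks within each of the four group-by-age cells, which gives 15 children per sequence in a full cell of 30. Record the order actually used. Estimate the position effect with a period term, for example a GEE or mixed logistic model with position and period, or the Mainland–Gart test for the binary end point. Show results by sequence as well, because a period term does not remove carry-over that differs between sequences. State in the protocol that instructions are the same in both positions.

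The cost is an allocation list and a short amendment; the number of tests and children is unchanged. One practical point needs the department's judgement. The Background section says that the supine position with eye contact makes cooperation easier, and it does not discuss whether the youngest children can start sitting.

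If the fixed order has to stay, the protocol should give the reason, state that position and order are confounded, and describe the primary result as the difference between a first lying and a second sitting test rather than as an effect of position.
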